4.1.2.4 Determination of the Recommended Dose or Maximum Tolerated Dose

The MTD and/or RD of FPA150 monotherapy and FPA150 combined with pembrolizumab for Phase 1a will be identified based on an evaluation of the overall safety, tolerability, pharmacodynamics, PK, and preliminary efficacy. The RD will take into account toxicities observed both during and beyond the DLT evaluation period as well as dose reductions and discontinuations due to toxicity that do not meet the DLT criteria. The RD, therefore, may or may not be the same as the identified MTD. For example, if the MTD is not reached, or if data from subsequent cycles of treatment from Phase 1a provide additional insight on the safety profile, then the RD may be a different, though not higher, dose than the MTD.

The MTD will be at a dose level where $\leq 1/3$ -6 patients reported a DLT. The RD will be a dose where $\leq 1/6$ patients reported a DLT, but may be lower than the MTD.

In the event that no MTD is identified and drug exposure exceeds what is deemed necessary based on nonclinical pharmacology data or the clinical PK and pharmacodynamic data (if available), the Sponsor and the Investigators may make a decision to discontinue dose escalation.

4.1.3 Study Design: Phase 1a Dose Exploration

Phase 1a includes a dose exploration cohort that may enroll beyond 3 patients (up to 20 additional patients across all dose levels). This 20 patients include 10 patients whose tumors express high levels of B7-H4 protein (3 mg and 10 mg), to further evaluate safety, PK, pharmacodynamics, and clinical activity at that dose (to be conditional upon the dose level clearing DLT criteria) of FPA150 monotherapy. It also includes up to 10 patients selected to have varying levels of B7-H4 expression [REDACTED] dosed at the FPA150 monotherapy MTD/RD.

Table 7: Proposed Dose Cohort/Level for Phase 1a Dose Exploration

Cohort	Dose/Regimen	B7-H4 Status
1aE1	FPA150 3 mg/kg	High
1aE2	FPA150 10mg/kg	High
1aE3	FPA150 monotherapy MTD/RD	

Abbreviations: MTD = maximum tolerated dose; Q3W = once every 3 weeks; RD = recommended dose

Toxicities observed in these patients will contribute to the overall assessment of safety and tolerability, but will not be included in the formal DLT calculations per Protocol [Table 5](#).

4.1.4 Study Design: Phase 1b Dose Expansion

Enrollment in Phase 1b monotherapy and in combination with pembrolizumab will begin when the MTD and/or RD has been identified by the CRC (refer to Section [4.1.1](#)), based on overall safety, tolerability, objective response, PK, pharmacodynamics from the Phase 1a part of the study.

Phase 1b will consist of tumor-specific cohorts of up to 30 patients each.

Requirements for archival tumor tissue and fresh biopsies by study phase are listed in Section [4.1](#). Separate ICFs for patients will be required regarding provision of fresh biopsies.

During the Screening Period, the patient will undergo protocol-specified screening procedures to ensure all eligibility criteria are met. Enrollment in Phase 1b will initially occur in 3 monotherapy cohorts and one cohort with FPA150 in combination with pembrolizumab (once the Safety Lead-in is completed and the MTD/RD for the combination is identified) as outlined in Table 8.

Table 8: Phase 1b Expansion Cohorts and Tumor Types

Cohort	Tumor Type	Therapy Type (Monotherapy or Combination)
1b1	Breast cancer	Monotherapy: FPA150
1b2	Ovarian cancer	Monotherapy: FPA150
1b3	Endometrial cancer	Monotherapy: FPA150
1bC1	Ovarian cancer	Combination: FPA150 with pembrolizumab

4.2 Number of Patients

The total number of patients planned for this study is estimated to be approximately 278.

Phase 1a will enroll approximately 68 patients depending on incidence of DLTs; this number of 68 patients includes:

- Up to 23 to 26 patients in the Phase 1a Dose Escalation and
- Up to 6 to 22 patients in the FPA150 and pembrolizumab combination Safety Lead-in and
- Allows for up to 20 additional patients in 2 cohorts in Phase 1a Dose Exploration.

Phase 1b will enroll up to 210 patients with specific tumor types with B7-H4 expression levels determined by IHC; this number of 210 patients includes:

- Up to 30 patients planned for each of three monotherapy expansion cohorts (refer to [Table 8](#)) and one FPA150 in combination with pembrolizumab cohort.
- Additional tumor type-specific cohorts may be enrolled based on emerging data. No individual expansion cohort will exceed 30 patients.

4.3 Patient and Study Completion

The duration of study for an individual patient includes screening (up to 28 days), treatment and an End of Treatment (EOT) follow-up period which will include visits at approximately 28 (± 7) days and 100 (± 7) days after the last dose. Since all patients are eligible to be treated until disease progression, the actual treatment duration for each individual patient will vary depending on the anticipated time to progression for their respective tumor type. Treatment beyond disease progression may be allowed in patients with initial Response Evaluation Criteria in Solid Tumors version 1.1 (RECIST v1.1) defined progressive disease if the benefit/risk assessment favors continued administration of study treatment (eg, patients are continuing to experience clinical benefit as assessed by the Investigator, and tolerating treatment).

In addition, patients enrolled in Phase 1b Dose Expansion will be followed for survival (including scans and survival status every 12 weeks [Q12W]) for up to 2 years).

4.4 End of Study Definition

The study will end when the last patient enrolled completes the EOT follow-up period. The EOT follow-up period will include visits at approximately 28 (± 7) days and 100 (± 7) days after the last dose.

4.5 Scientific Rationale for Study Design

This is a Phase 1a/1b study. Phase 1a includes an accelerated titration design followed by standard 3+3 dose escalation design in unselected solid tumor patients. Once MTD/RD of FPA150 monotherapy is identified a cohort of patients will be enrolled on a Phase 1a Safety Lead-in with FPA150 + pembrolizumab to determine the RD of FPA150 in the combination.

Phase 1a will also include the option of enrolling up to 20 additional patients at 1 or more dose levels with varying levels of B7-H4 expression. Fresh biopsies will be mandatory in these additional patients. This will enable a more robust exploration of safety, PK and pharmacodynamics at any dose level.

Phase 1b is a dose expansion portion in patients with advanced breast, ovarian, and endometrial cancer that will be selected based on B7-H4 expression. These tumor types have been identified based on their known high prevalence of B7-H4 expression (Section 2.1) and limited availability of effective therapies in the unresectable and metastatic setting. Based on the preclinical activity of FPA150 and PD-L1 inhibitors (see Section 2.2.2.2) Phase 1b will also include a cohort of the combination of FPA150 and pembrolizumab to evaluate safety, tolerability and preliminary efficacy. The initial tumor type to be evaluated with the combination will be ovarian cancer based on the high unmet need in this population, high expression of B7-H4 and the limited clinical benefit observed with anti-PD1 agents alone. Additional cohorts with different tumor types or combinations may be enrolled based on emerging clinical and translational data for this pathway and molecule. Phase 1b Dose Expansion will enable a more thorough investigation of the clinical and biological activity of FPA150 monotherapy and in combination with pembrolizumab in more homogenous patient groups (by tumor type and biomarker expression) and will help define further clinical development of this molecule.

Fresh pre-treatment and on treatment study biopsies are mandatory in at least 15 of 30 patients enrolled in each Phase 1b cohort which may provide insight into the mechanism of action of FPA150 and help further refine potential tumor tissue-based biomarkers. The primary endpoints for both the Phase 1a and Phase 1b portions are related to safety and tolerability and the statistical analyses will be descriptive. Additional details regarding the statistical assumptions for secondary endpoints related to evaluating preliminary efficacy in the 30-patient expansion cohort are described in Section 9.1.

4.6 Justification for Dose and Dosing Regimen

FPA150 is a glycoengineered IgG1 anti-B7-H4 monoclonal antibody with enhanced ADCC and checkpoint blockade activities, developed to be administered to patients with advanced solid tumors. The International Conference on Harmonization (ICH) S9 guidance (“Nonclinical Evaluation for Anticancer Pharmaceuticals”) is applied to select FPA150 starting dose in human. The proposed starting dose in this study is 0.01 mg/kg IV Q3W. This was calculated using the established dose selection guidelines for the MABEL approach

(Saber 2016). The design is an accelerated titration followed by standard 3+3 dose escalation with approximately half log dose escalations.

FPA150 will be administered via IV infusion Q3W, which is consistent with a schedule commonly used for humanized monoclonal antibodies with an expected half-life of approximately 10 to 20 days. The dose of FPA150 will be based on body weight at Cycle 1 Day 1. After Cycle 1, the FPA150 dose will be recalculated at each infusion visit only if the patient's weight has changed > 10% from Cycle 1, Day 1.

The proposed dose of pembrolizumab of 200 mg Q3W is consistent with the current approved US Prescribing Information. The initial starting dose of FPA150 in combination with pembrolizumab will be the RD identified during monotherapy dose escalation. This is an acceptable approach given the preliminary safety data of FPA150 monotherapy and the well characterized safety profile of pembrolizumab. Step down dosing of FPA150 in response to emerging safety data is planned.

4.7 Patient Selection

FPA150 is an antibody designed to recognize B7-H4 which is expressed highly on tumors, such as on breast cancer, ovarian cancer, and endometrial cancer. Because it is predicted that patients whose tumors have higher expression of the target B7-H4 protein are more likely to respond to FPA150, patients will undergo pre-screening to allow selection based on B7-H4 expression in the Phase 1a Combination Safety Lead-in, Phase 1a Monotherapy Dose Exploration and in Phase 1b Dose Expansion (Monotherapy and in combination with pembrolizumab).

Tumor samples (fresh or archival) from all patients will be assessed by IHC to determine the expression of B7-H4 protein, and patients in Phase 1b and a subset of patients in Phase 1a will be selected based on being positive for B7-H4.

5 Study Population

5.1 Inclusion Criteria

5.1.1 Phase 1a Inclusion Criteria (Monotherapy and Combination Therapy)

Patients enrolling into **Phase 1a** must meet *all* of the following inclusion criteria:

- 1) Histologically confirmed solid tumors except primary central nervous system (CNS) tumors.
- 2) Disease that is unresectable, locally advanced, or metastatic.
- 3) Able to understand and sign an IRB/IEC)approved ICF prior to any study-specific evaluation.
- 4) Patients should be refractory to or intolerant of existing therapy(ies) known to provide clinical benefit for their condition.
- 5) All patients must have at least one measurable lesion at baseline according to RECIST v1.1; tumor sites situated in a previously irradiated area, or in an area subjected to other loco-regional therapy, are not considered measurable unless there has been demonstrated progression in the lesion.
- 6) Adequate washout for prior anti-cancer therapy (ie, ≥ 5 half-lives or 4 weeks since the last dose, whichever is shorter).
- 7) Availability of archival tumor tissue for retrospective biomarker analysis, or patient must undergo a fresh tumor biopsy during screening if archival tissue is not available (a biopsy is required for patients in the Phase 1a Dose Exploration portion). Archival tissue for patients enrolled in Cohort 1b1 (Breast Cancer) must be within 24 months prior to pre-screening.
- 8) Age ≥ 18 years at the time the ICF is signed.
- 9) Eastern Cooperative Oncology Group (ECOG) performance status of 0 or 1.
- 10) Life expectancy of at least 3 months in the opinion of the Investigator.
- 11) Willing and able to comply with all study procedures.
- 12) Prior radiotherapy must be completed at least 2 weeks before the first dose of study drug.
- 13) Prior radiopharmaceuticals (eg, strontium, samarium) must be completed at least 8 weeks before the first dose of study drug.
- 14) Prior surgery that requires general anesthesia must be completed at least one week before first dose of study drug administration. Surgery requiring local/ epidural anesthesia must be completed at least 72 hours before first dose of study drug administration. Patients must have recovered from any surgery.

15) Screening laboratory values must meet the following criteria:

Hematologic:

- a. Neutrophils ≥ 1200 cells/ μ L
- b. Platelets $\geq 75 \times 10^3/\mu$ L
- c. Hemoglobin (Hb) ≥ 9.0 g/dL

Renal:

- d. Serum creatinine $< 1.5 \times$ ULN or creatinine clearance (CrCl) of ≥ 40 mL/minute (using Cockcroft/Gault Formula)

$$\text{Female CrCl} = \frac{(140 - \text{age in years}) \times (\text{weight in kg}) \times 0.85}{72 \times (\text{serum creatinine in mg/dL})}$$

$$\text{Male CrCl} = \frac{(140 - \text{age in years}) \times (\text{weight in kg})}{72 \times (\text{serum creatinine in mg/dL})}$$

Hepatic:

- e. AST and ALT $\leq 3 \times$ ULN (AST and ALT $< 5 \times$ ULN in patients with liver metastases is permitted)
 - f. Bilirubin $< 1.5 \times$ ULN (except patients with Gilbert's syndrome, who must have total bilirubin < 3 mg/dL)
- 16) Negative serum β -human chorionic gonadotropin (β -hCG) pregnancy test ≤ 96 hours prior to treatment on Cycle 1, Day 1 (women of childbearing potential only).
- 17) In sexually active patients (women of child bearing potential and males), willingness to use 2 effective methods of contraception, of which 1 must be a physical barrier method (condom, diaphragm, or cervical/vault cap) until 6 months after the last dose of FPA150. Other effective forms of contraception include:
- Permanent sterilization (hysterectomy and/or bilateral oophorectomy, or bilateral tubal ligation with surgery, or vasectomy) at least 6 months prior to Screening
 - Women of childbearing potential who are on stable oral contraceptive therapy or intrauterine or implant device for at least 90 days prior to the study, or abstain from sexual intercourse as a way of living

50) For Phase 1a Combination Safety Lead-in Patients ONLY:

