Dosing: FPA150 will be administered as a single agent in a 60-minute (± 5 minutes) IV infusion Q3W, on Day 1 of each 21-day cycle. The dose of FPA150 will be based on body weight at Cycle 1 Day 1 (C1D1). After Cycle 1, the FPA150 dose will be recalculated at each infusion visit only if the patient's weight has changed $> 10\%$ from Cycle 1, Day 1. There is no pre-specified maximum number of doses of FPA150 for patients receiving monotherapy.

Patients may continue receiving FPA150 monotherapy according to their study specified cohort/dose until Investigator-assessed clinical progressive disease, unacceptable toxicity, or the patient meets any of the other protocol-specified withdrawal criteria (refer to Section 7).

For combination cohorts, pembrolizumab will be administered at a dose of 200 mg IV over 30 minutes (\pm 5 minutes) starting on C1D1 after the completion of FPA150 infusion. Dosing for combination cohorts will be repeated on Day 1 of each 21-day cycle. Patients in the combination cohort may receive one or both drugs in combination according to their study specified cohort/dose until Investigator-assessed clinical progressive disease, unacceptable toxicity, or the patient meets any of the other protocol-specified withdrawal criteria (refer to Section 7). Patients treated with the combination would be able to receive pembrolizumab treatment for up to 24 months. If one of the two drugs has to be discontinued, patients may continue to receive the other drug alone.

Treatment beyond disease progression may be allowed in patients with progressive disease according to Response Evaluation Criteria in Solid Tumors version 1.1 (RECIST v1.1) if the benefit/risk assessment favors continued administration of study treatment (eg, if patients are continuing to experience clinical benefit as assessed by the Investigator, and tolerating treatment).

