5% irrespective of PD-L1 status (Adams 2017). The combination of atezolizumab and nab-paclitaxel in frontline metastatic TNBC patients showed improvement in median OS compared to nab-paclitaxel alone. However the benefit was predominately observed in PD-L1 positive patients (HR 0.62) compared to all patients (HR 0.84) suggesting low efficacy in PD-L1 negative patients (Schmid 2018). Patients with recurrent or metastatic endometrial carcinoma who experience progressive disease on frontline chemotherapy have a poor prognosis with median OS of less than 1 year. For example, patients treated with the anti-vascular endothelial growth factor (VEGF)-A monoclonal antibody bevacizumab after failure of 1 or 2 lines of chemotherapy reported a median PFS of 4.2 months and median OS of 10.5 months (Aghajanian 2011). Patients with early platinum-refractory, recurrent or metastatic ovarian cancer have a median OS of 13 to 16 months and median PFS of 3 to 6 months with single agent chemotherapy with or without bevacizumab (Pujade-Lauraine 2014). Median PFS and OS significantly diminish in patients with multiply relapsed disease (Hanker 2012). Immunotherapy has demonstrated limited activity to date in this tumor type (Hamanishi 2015). Therefore, significant unmet need still exists in these tumor types particularly in the metastatic setting after failure of standard frontline therapy.

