5.2 Eligibility Criteria

Exclusion Criteria (Phase 1a And Phase 1b)

Patients who meet ANY of the following criteria will be excluded from study entry:

- 1) Immunosuppressive doses of systemic medications, such as steroids or absorbed topical steroids (doses > 10 mg/day prednisone or equivalent daily) must be discontinued at least two weeks before the first dose of study drug. Short courses of high dose steroids, continuous low dose (prednisone < 10 mg/day), inhaled, intranasal, intraocular, and joint injections of steroids are allowed
- 2) Decreased cardiac function with New York Heart Association (NYHA) > Class 2 at screening
- 3) Uncontrolled or significant heart disorder such as unstable angina
- 4) QT interval corrected for heart rate (QTc) per institutional guidelines > 450 msec for males or > 470 msec for females at screening
- 5) History of ADAs, , severe allergic, anaphylactic, or other infusion-related reaction to a previous biologic agent
- 6) Known hypersensitivity to any component of the investigational product (IP) formulation including active ingredient, sodium acetate, sucrose, and polysorbate 20 (refer to Section [6.1.1](#))

- 7) Vaccines (eg, human papilloma virus [HPV] vaccine) within 4 weeks before the first dose of study drug. The inactivated seasonal influenza vaccine can be given to patients before treatment and while on therapy without restriction. Influenza vaccines containing live virus or other clinically indicated vaccinations for infectious diseases (ie, pneumovax, varicella, etc.) may be permitted, but must be discussed with the Sponsor's Medical Monitor and may require a study drug washout period prior to and after administration of the vaccine.
- 8) Current unresolved infection or history of chronic, active, clinically significant infection (viral, bacterial, fungal, or other) which, in the opinion of the Investigator, would preclude the patient from exposure to a biologic agent or may pose a risk to patient safety.
- 9) Patients with abnormal serum chemistry values that in the opinion of the Investigator are considered to be clinically significant. This includes patients who show clinical signs and symptoms related to their abnormal serum chemistry values, as well as patients whose serum chemistry values are asymptomatic, but clinically significant according to the Investigator (eg, hypokalemia or hyponatremia).

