6.5 Maximum Duration of Treatment

There is no pre-specified maximum number of doses of FPA150 monotherapy or in combination. Patients may continue receiving FPA150 monotherapy according to their study specified cohort/dose until Investigator-assessed disease progression or the patient meets any of the other protocol-specified withdrawal criteria.

Patients may receive pembrolizumab therapy according to their study specified cohort/dose until Investigator-assessed disease progression, the patient meets any of the other protocol-specified withdrawal criteria or the patient completes approximately 24 months of pembrolizumab treatment.

If one of the two drugs have to be discontinued, patients may continue to receive the other drug alone.

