8.7.1 Pregnancy Testing

Pregnancy is an exclusion criterion and women of child bearing potential must not be considering pregnancy during the study. Pregnancy tests should be performed for any woman of childbearing potential. Serum β -hCG (evaluated by local laboratories) and urine pregnancy tests will be performed only on women of child bearing potential.

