8.7.2 Pregnancy on Study

In the event of suspected pregnancy, a serum pregnancy test should be repeated. Patients who become pregnant during the study must discontinue study treatment immediately.

The Sponsor must be notified of any patient who becomes pregnant while participating in this study. Although pregnancy is not an AE, all pregnancies must be followed to conclusion to determine their outcome. It is the responsibility of the Investigator or designee to report any pregnancy in a patient that occurs during the study by completing the Pregnancy Reporting Form. Please contact the study monitor to receive the Pregnancy Reporting Form on learning of a pregnancy.

Notification of the pregnancy including the anticipated date of birth should be submitted on a Pregnancy Reporting Form within 24 hours of awareness and reported using the same procedure as described for reporting SAEs (Section 8.12.6). If the pregnancy is to be terminated, the anticipated date of termination should be provided.

The patient will be asked to provide information on the outcome of the pregnancy, including premature termination should the case arise. Spontaneous miscarriages, premature termination of the pregnancy, and congenital abnormalities will be reported as SAEs. Information on the status of the mother and child will be forwarded to the Sponsor. Follow-up will be in accordance with regulatory guidance and at least 6 to 8 weeks after the estimated delivery date.

Pregnancies that occur during the first 6 months of the Follow-up period should be reported to the Sponsor, and followed as described above.

Refer to https://www.merck.com/product/usa/pi_circulars/k/keytruda/keytruda_pi.pdf for additional guidelines regarding pregnancy and contraception for pembrolizumab.

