- i. B7-H4 expression results must be available prior to enrollment for all patients in Phase 1a Monotherapy Dose Exploration, Phase 1a Combination Safety Lead-in, and all patients in Phase 1b Dose Expansion (monotherapy and in combination with pembrolizumab). Archival tissue for patients enrolled in Cohort 1b1 (Breast cancer) must be within 24 months prior to pre-screening. Five unstained sections from an archival tumor block must be provided during pre-screening of patients in Phase 1a Dose Exploration and in Phase 1b Dose Expansion for evaluation of B7-H4 expression by IHC. Archival tumor block (preferred) or 10 unstained sections from an archival tumor block must be provided during screening in all patients for exploratory biomarker analyses.
- j. **Refer to Appendix 5 for a listing of all Clinical Safety Laboratory Tests to be conducted.** Local hematology and blood chemistry test results must be obtained within 96 hours of dosing to confirm eligibility. **All serum chemistries will be assessed locally.**
- k. CT/MRI of the tumor sites should be measured according to RECIST v1.1. Tumor assessment should be performed at screening, then every 6 weeks [± 1] week for the first 6 months for patients who remain on treatment (and every 12 [± 2] weeks, thereafter). If patient terminates prior to scheduled CT/MRI scans, patient should have scans done at the EOT visits (does not need to be repeated if performed within 6 weeks prior to the End of Treatment visits, or if tumor progression was previously determined). Patients who enter LTFU while showing clinical benefit should have tumor assessments Q12W for DOR. The same measuring modality should be used by the site to maintain consistency across the various time points.
- l. Tumor markers will be assessed at a central laboratory. Tumor markers will be collected Day 1 of Cycles 1, 2, 3, 4, 5, 7, and 9. After Cycle 9 tumor markers will be collected every 12 weeks (every 4 cycles). Tumor markers will be collected at the times noted in [Appendix 2](#).

- m. All women of childbearing potential (including those who have had a tubal ligation) will have a serum pregnancy test at screening. A serum or urine pregnancy test will be performed at Cycle 1 Day 1 and every 6 weeks during treatment, and at the EOT visits.

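### Two eligibility criteria were not adapted to the pembrolizumab combination: the contraception period runs only from the last FPA150 dose, and exclusion 6 names pembrolizumab in the synopsis but not in Section 5.2

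*Protocol*

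**What the plan says.** **Contraception.** Criterion 17, worded alike on this point in the synopsis and Section 5.1.1, asks sexually active patients to use two effective methods, one of them a barrier, "until 6 months after the last dose of FPA150". The heading of Section 5.1.1 covers monotherapy and combination therapy. Criterion 18 carries criterion 17 into Phase 1b, since it excepts only criterion 1.

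**Treatment duration.** Section 6.5 states: "If one of the two drugs have to be discontinued, patients may continue to receive the other drug alone". The synopsis (Dosing) adds: "Patients treated with the combination would be able to receive pembrolizumab treatment for up to 24 months". Section 8.14 repeats both points.

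**Other pregnancy provisions.** Section 8.7.1 says that "women of child bearing potential must not be considering pregnancy during the study". Footnote m to the Schedule of Assessments (Appendix 1) requires a pregnancy test at Cycle 1 Day 1 and then "every 6 weeks during treatment, and at the EOT visits". Under Section 8.7.2 a patient who becomes pregnant stops treatment at once, and sites are referred to the prescribing information "for additional guidelines regarding pregnancy and contraception for pembrolizumab".

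**Exclusion 6.** Section 5.2 reads "Known hypersensitivity to any component of the investigational product (IP) formulation including active ingredient, sodium acetate, sucrose, and polysorbate 20" and cross-refers to Section 6.1.1, which describes FPA150. The synopsis version of the same criterion names the FPA150 formulation and then adds pembrolizumab. Section 8.1 enrols patients against the criteria in Section 5.

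**The concern.** Both criteria still follow FPA150 alone, although Amendment 2 added a second drug that can outlast it. A woman of childbearing potential who stops FPA150 and continues pembrolizumab can reach the end of her contraception commitment while on active treatment. Even if the commitment outlasts dosing, the cover after her last pembrolizumab dose is shorter than the 6 months the protocol sets for FPA150. The stake is fetal exposure.

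For exclusion 6, a site screening a combination candidate has two texts under one number. The one in the section that governs enrolment does not name the second drug, so a patient with a known allergy to a pembrolizumab excipient could be judged eligible. The settings concerned are the Phase 1a combination safety lead-in and cohort 1bC1. DLT decisions, sample size and the efficacy analysis are not touched.

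**Working it through.** The plan gives no figure to reproduce. The first part needs date arithmetic and the second a comparison of texts.

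**Part 1: contraception period**

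Inputs from the protocol:
- Contraception ends 6 months after the last FPA150 dose (criterion 17).
- Pembrolizumab may continue alone, to about 24 months (Section 6.5, synopsis).
- FPA150 can stop early. Section 6.4.6 ends it permanently after infusion-associated events of Grade 3 or above. Section 6.4.4 ends it after any related Grade 4 toxicity, after Grade 3 toxicity that does not recover within 28 days, or if a dose reduction is needed in the DLT period.

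The protocol does not say when patients will stop each drug, so these are assumed over a range: m is the month of the last FPA150 dose and T the month of the last pembrolizumab dose, both counted from the start of treatment.

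Uncovered time on pembrolizumab = max(0, T − (m + 6)) months:

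| m | T = 6 | T = 12 | T = 24 |
|---|---|---|---|
| 0 | 0 | 6 | 18 |
| 3 | 0 | 3 | 15 |
| 6 | 0 | 0 | 12 |
| 12 | – | 0 | 6 |
| 18 | – | – | 0 |

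For example, T = 24 and m = 3 gives 24 − (3 + 6) = 15. The row m = 0, a patient who receives a single FPA150 dose, is the extreme case.

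Cover left after the last pembrolizumab dose = max(0, 6 − (T − m)) months:
- both drugs stop together: 6 − 0 = 6;
- pembrolizumab continues 2 months longer: 6 − 2 = 4;
- pembrolizumab continues 6 months or more: 0.

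So a gap during dosing needs more than 6 months of pembrolizumab alone, but any period on pembrolizumab alone shortens the cover afterwards.

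If the period were counted from the later last dose, uncovered dosing time would be 0 for every m and T. With 6 months kept for illustration, cover after pembrolizumab would always be 6 months.

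**Part 2: exclusion 6**

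- Synopsis: the FPA150 formulation and/or pembrolizumab.
- Section 5.2: the investigational product formulation, with FPA150's active ingredient and excipients listed and a reference to Section 6.1.1. The abbreviation list defines IP as FPA150 or placebo.
- FPA150 excipients (Section 6.1.1): sodium acetate, sucrose, polysorbate 20.
- Pembrolizumab excipients (Section 6.1.2): L-histidine, polysorbate 80, sucrose, water.

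Sucrose is common to both. L-histidine and polysorbate 80 are in pembrolizumab only. Known allergy to pembrolizumab itself should be rare, because criteria 50.04 and 24.03 bar prior anti-PD1 or PD-L1 therapy, and exclusion 5 covers severe allergic or infusion-related reactions to an earlier biologic. What is left is mainly an excipient allergy learned from another product.

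**The case against.** **The label handles contraception.** The protocol consistently defers pembrolizumab matters to its prescribing information: storage, preparation, toxicity management, infusion reactions. Section 8.7.2 does the same for contraception. Together with the rule against considering pregnancy, regular testing and immediate discontinuation, this means the protocol is not silent. That is fair, and it lowers the risk. But the reference sits under the heading for pregnancies on study, states no period and leaves criterion 17 as it is. The rule in Section 8.7.1 names no method. Testing and discontinuation act only after conception. The label and the consent pages were not available for this review, so they may close the gap in practice; the protocol text does not.

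**Almost nobody is exposed.** The patient must have recurrent ovarian, peritoneal or tubal cancer, usually after two regimens, and still be of childbearing potential and sexually active. She must also stop FPA150 but not pembrolizumab, and go on for more than 6 months. Section 2.1 cites "median PFS of 3 to 6 months with single agent chemotherapy with or without bevacizumab" for early platinum-refractory, recurrent or metastatic disease, shorter times after multiple relapses, and limited immunotherapy activity. Section 2.2.5 reports no DLTs, no dose reductions and one related Grade 3 event in 24 patients on monotherapy. This stands: long gaps would be uncommon. It is not a cap, since treatment beyond progression is allowed.

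**Exclusion 6 is only a mismatch, and the stricter text is in the synopsis.** The placebo in the IP definition looks like a template remnant in an open-label study. The synopsis uses its investigational product heading for both drugs, and the list in Section 5.2 need not be exhaustive. The term is therefore less clear-cut than the abbreviation list suggests. But the cross-reference in Section 5.2 goes to FPA150 only, and Section 8.1 sends sites to Section 5. A conscientious site would probably apply the synopsis, but it should not have to choose.

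**Conclusion.** Both points hold. As written, the contraception commitment for combination patients can end during pembrolizumab dosing, and Section 5.2 omits a drug that the synopsis includes.

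The size is small. At most 22 lead-in patients and 30 patients in 1bC1 (22 + 30 = 52) are in the cohorts concerned. The contraception gap affects an unstated, probably very small subset of them. For that subset the uncovered dosing time runs from 0 to 18 months over the assumed range of stopping times, with the upper end unlikely given the progression times the protocol cites. The hypersensitivity gap is narrower still, mainly L-histidine and polysorbate 80.

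This is a patient-safety and consistency point that should be corrected because the possible harm is serious and the correction is simple. It has no effect on error rates, estimates or dose decisions. The conclusion rests on the protocol text; the consent form and the pembrolizumab label could add protection that was not visible here.

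**What to change.** 1. In criterion 17 (synopsis and Section 5.1.1), for the combination cohorts, count the end of contraception from the last dose of FPA150 or pembrolizumab, whichever is later. The sponsor should set the length, consistent with the pembrolizumab prescribing information.
2. Use one text for exclusion 6 in the synopsis and Section 5.2. For the combination cohorts it should cover pembrolizumab and the formulation components listed in Section 6.1.2.

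The cost is two wording changes in the protocol, and a matching change in the consent form if it repeats criterion 17. A few patients take on a longer contraception commitment, and there may be a rare extra screen failure.
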